## CLINICAL TRIAL PROTOCOL SYNOPSIS

Name of company: Boehringer Ingelheim(BI)		Tabulated Trial Protocol	
Name of finished product: Tradjenta®, Trajenta®, Trayenta®, Trazenta®			
Name of active ingredient: linagliptin			
Protocol date: 15 May 2014	Trial number: 1218.149		Revision date: 16 October 2015
Title of trial:	A 24 week randomized, double-blind, placebo-controlled, parallel group, efficacy and safety trial of once daily linagliptin, 5 milligrams orally, as add on to basal insulin in elderly Type 2 Diabetes Mellitus patients with insufficient glycaemic control		
Co-ordinating Investigator:	[REDACTED]		
Trial sites:	A multi-centre trial to be conducted in multiple countries		
Clinical phase:	Phase IV		
Objectives:	To investigate the efficacy, safety, and tolerability of linagliptin 5 milligrams (mg) once a day (q.d.) compared to placebo as add-on therapy for 24 weeks to stable basal insulin treatment in elderly ( $\geq 60$ years old) patients with Type 2 Diabetes Mellitus (T2DM) with insufficient glycaemic control		
Methodology:	Randomised, double-blind, multi-national, placebo-controlled, parallel design comparison as add-on therapy to a stable background of basal insulin, metformin (optional), and/or alpha-glucosidase inhibitors (optional) over 24 weeks.		
No. of patients:			
total entered:	Entered (into the double-blind treatment period): approximately 300		
each treatment:	1:1 allocation ratio per treatment arm [i.e., 150 patients assigned to linagliptin 5mg q.d. and 150 patients assigned to placebo matching linagliptin 5 mg q.d.]		
Diagnosis:	Elderly ( $\geq 60$ years old) T2DM patients with glycated (or glycosylated) haemoglobin (HbA 1c ) levels of 7.0% to 10.0% at Screen who are on a stable background antidiabetic therapy of basal insulin, metformin (optional), and/or alpha-glucosidase inhibitor (optional).		
Main criteria for inclusion:	T2DM patients who are 60 years of age or older: 
 
• with HbA1c levels of 7.0% to 10.0% at Screen
 
• taking stable doses of basal insulin at least 4 weeks prior to randomisation, and metformin (optional) and/or alpha-glucosidase inhibitor (optional) at least 12 weeks prior to randomization
 
• with a Body Mass Index (BMI) of less than or equal to 45 kilograms per meters squared (<math>\leq 45 \text{ kg/m}^2</math>)
 
		

Proprietary confidential information.

© 2015 Boehringer Ingelheim International GmbH or one or more of its affiliated companies. All rights reserved.

This document may not - in full or in part - be passed on, reproduced, published or otherwise used without prior written permission.

Name of company: Boehringer Ingelheim(BI)		Tabulated Trial Protocol	
Name of finished product: Tradjenta®, Trajenta®, Trayenta®, Trazenta®			
Name of active ingredient: linagliptin			
Protocol date: 15 May 2014	Trial number: 1218.149		Revision date: 16 October 2015
Test product(s):	linagliptin tablet		
dose:	5 mg (tablet strength)		
mode of admin.:	by mouth (p.o.) each morning		
Comparator products:	placebo tablet (matching linagliptin)		
dose:	Not Applicable (N/A)		
mode of admin.:	p.o.		
Duration of treatment:	A one week Screen period with no study medication, leading into a one week placebo Run-In period, followed by a double-blind treatment period for 24 weeks, and a one week post-treatment period with no study medication.		
Criteria for efficacy:	
The primary endpoint is the change from baseline in HbA1c after 24 weeks of treatment.
 
Secondary endpoints are the following:
 
 
• Proportion of patients experiencing at least one confirmed hypoglycaemic event during 24 weeks of treatment.
 
• Proportion of patients with HbA1c on treatment <8.0% after 24 weeks of treatment
 
• Proportion of patients with HbA1c on treatment <7.0% after 24 weeks of treatment
 
• Proportion of patients with HbA1c lowering by at least 0.5% after 24 weeks of treatment
 
• Change from baseline in Fasting Plasma Glucose (FPG) after 24 weeks of treatment
 
		
Criteria for safety:	Adverse events (including relevant new or worsening pre-existing conditions) and hypoglycaemic events		
Statistical methods:	Restricted maximum likelihood estimation based on mixed-effect model for repeated measures analysis will be used to obtain adjusted means for the treatment effects. This model will include treatment, baseline insulin dose, and week as discrete fixed effects, baseline HbA 1c as a continuous fixed effect, interaction between week and treatment, and interaction between week and baseline HbA 1c . The primary treatment comparisons will be the contrast between treatments at Week 24.		

Proprietary confidential information.

© 2015 Boehringer Ingelheim International GmbH or one or more of its affiliated companies. All rights reserved.

This document may not - in full or in part - be passed on, reproduced, published or otherwise used without prior written permission.

If a visit window (+/- 7 days: i.e., 1 day to 7 days) is used after randomisation, the patient should be returned to the original trial schedule by the next visit (i.e., the number of visit window days used must be subtracted from the upcoming visit). This procedure ensures that all patients complete: the treatment period at approximately Day 169 and the Post-Treatment Visit at approximately Day 176. The visit window between Visits 98 and 99 will not be allowed once trial enrolment has been achieved (sufficient patients screened to randomise **300 with 100 from Japan**); the Clinical Monitor Local (CML) will inform trial sites when trial enrolment is complete.

B Functional reviews (Patient Health Questionnaire and Saint Louis University Mental Status Examination) will be completed first to assess the functional ability, mental health, and cognitive ability of potential patients. For the Screen Visit: the screening evaluations (except for the Patient Health Questionnaire, Saint Louis University Mental Status Examination, and HbA1c which must be completed in this order immediately after informed consent) may be completed on separate days as long as the results are obtained within the allowed days for the visit.

C In the event of any cardiac symptoms (i.e., suspicion of heart rhythm disorders or cardiac ischemia) at Visit 1, Visit 3 and/or Visit 98, an additional follow-up ECG will be collected and recorded after that particular visit.

D Fasting blood samples (no food and/or drink except for water 10 hours prior to visit) via central lab. Starting at Visit 3, if hyperglycaemia is noted, repeat FPG via central lab.

[REDACTED]

F Exception: For the Screen Visit only, patients do not have to be fasting.

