### **3.2 DISCUSSION OF TRIAL DESIGN, INCLUDING THE CHOICE OF CONTROL GROUPS**

Due to its mechanism of action and the low risk for hypoglycaemia induction, DPP-4 inhibitors like linagliptin should provide additional efficacy alongside manageable tolerability and safety in elderly patients when added to background antidiabetic therapy consisting of basal insulin, metformin (optional), and/or alpha-glucosidase inhibitors (optional).

Elderly patients with T2DM who have insufficient glycaemic control will enter the trial and receive either double-blind linagliptin or placebo. The placebo-controlled design is considered ethically acceptable on the basis of the benefit and risk assessment, as defined in [Section 2.3](#); appropriate criteria for patient discontinuation, ability to adjust or change permitted antidiabetic therapy to maintain, or obtain sufficient level of glycaemic control, as defined in [Section 4.2.1](#); and relevant local and regional guidelines for optimized standard of care.

The randomised treatment period is planned for 24 weeks because the primary efficacy endpoint of HbA1c has been shown to reflect glycaemic control over the preceding 12 weeks and this period should allow sufficient time to demonstrate changes in the incidence of hypoglycaemia events. The 1-week Post-Treatment period is considered to be sufficient, as previous trials with linagliptin have shown that the pharmacodynamic effect of linagliptin only extends to about 7 days after the last dose.

The permitted background antidiabetic therapy will not be provided as part of the clinical trial supplies, unless required by local laws and regulations.

The rationale for dose and dose-interval selection is described in [Section 4.1.3](#).

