#### 5.2.2.2 Adverse event and serious adverse event reporting

All adverse events, serious and non-serious, occurring during the course of the clinical trial (i.e., from signing the informed consent onwards through the last per protocol contact) will be collected, documented and reported to the sponsor by the investigator on the appropriate

Proprietary confidential information.

© 2015 Boehringer Ingelheim International GmbH or one or more of its affiliated companies. All rights reserved.

This document may not - in full or in part - be passed on, reproduced, published or otherwise used without prior written permission.

eCRFs / SAE reporting forms. Reporting will be done according to the specific definitions and instructions detailed in the ‘Adverse Event Reporting’ section of the ISF.

The residual effect period (REP), defined as the period of time after the last dose of medication when measurable drug levels or pharmacodynamic effects are still likely to be present, for linagliptin is 7 days. Therefore all events reported within 7 days of the last trial medication will be considered on-treatment. The follow-up period, defined as the period between the last medication and the last per protocol visit, is 7 days.

Reporting will be done according to the specific definitions and instructions detailed in the ‘Adverse Event Reporting’ section of the ISF.

For each adverse event, the investigator will provide the onset date, end date, intensity, treatment required, outcome, seriousness, and action taken with the investigational drug. The investigator will determine the relationship of the investigational drug to all AEs as defined in [Section 5.2.2.1](#).

The investigator does not need to actively monitor patients for adverse events once the clinical trial has ended. However, if the investigator becomes aware of an SAE(s) that occurred after the patient has completed the clinical trial (including any protocol required REP and / or follow-up period), it should be reported by the investigator to the sponsor if considered relevant by the investigator.

All AEs and/or SAEs, including those persisting after trial completion, must be followed up until they have resolved, have been sufficiently characterized, or no further information can be obtained.

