## 6. INVESTIGATIONAL PLAN

### 6.1 VISIT SCHEDULE

All trial visits should be routinely scheduled in the morning, at approximately the same time of day (07:00 AM to 11:00 AM). If a patient mistakenly takes study medication on the morning of a visit before attending the clinic (excluding visits starting before randomisation) or comes in non-fasted where a fasting condition is required (all visits except Screen), the visit should be rescheduled for another day as soon as possible reminding the patient about the expected conditions. The rescheduled visit must take place within the allowed visit window (i.e., in less than 7 days) so that the patient has sufficient study medication.

All patients are to adhere to the visit schedule as specified in the [Flow Chart](#). If any visit has to be rescheduled, subsequent visits should follow the original visit date schedule. The study medication bottles contain sufficient medication to allow for these time windows.

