#### Premature discontinuation from the trial (between Visits 98 and 99)

If a patient discontinues after the 24-week treatment period, the patient should return to the trial site for Visit 99 (the Post-Treatment Visit that occurs 7 days after Visit 98), which will be performed as a trial visit.

The investigator may initiate any additional antidiabetic therapy based on his or her discretion no sooner than one day after discontinuing study medication.

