7.8.1 Adverse events

Unless otherwise specified, the analyses of AEs will be descriptive in nature. All analyses of AEs will be based on the number of patients with AEs and NOT on the number of AEs.

Furthermore, for analysis of AE attributes such as duration, severity, etc. multiple AE occurrence data on the CRF, will be collapsed into AE episodes provided that all of the following applies:

- The same MedDRA lowest level term was reported for the occurrences.
- The occurrences were time-overlapping or time-adjacent (time-adjacency of 2 occurrences is given if the second occurrence started on the same day or on the day after the end of the first occurrence).
- Treatment did not change between the onset of the occurrences OR treatment changed between the onset of the occurrences, but no deterioration was observed for the later occurrence.

For further details on summarisation of AE data, please refer to the guideline 'Handling and summarization of AE data for clinical trial reports and integrated summaries' ([2](#)).

The analysis of AEs will be based on the concept of treatment emergent AEs. That means that all AEs occurring between first drug intake until 7 days after last drug intake will be assigned to the randomised treatment; in these cases the date and time of the AE onset are used. All AEs occurring before first drug intake will be assigned to 'screening' and all adverse events occurring after last drug intake + 7 days will be assigned to 'post-treatment' (for listings only). For details on the treatment definition, see [Section 6.1](#). Japanese patients who did not prematurely discontinue prior or at day 175 do not have a post-treatment period for Week 24 analysis.

According to International Conference on Harmonisation (ICH) E3 ([3](#)) AEs classified as 'other significant' will include those non-serious adverse events with

- 'action taken = discontinuation' or 'action taken = reduced', or

- marked haematological and other lab abnormalities or lead to significant concomitant therapy as identified by the Clinical Monitor/Investigator at a Blinded Report Planning Meeting.

An overall summary of AEs will be presented. In addition, the frequency of patients with adverse events will be summarised by treatment, primary system organ class and preferred term. Separate tables will be provided for patients with other significant adverse events according to ICH E3 (3) for patients with serious adverse events, AELDs, AEs by severity, and AEs by outcome.

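### For non-Japanese completers with a late Visit 98 before enrolment closes, the return-to-schedule rule shortens the week before Visit 99 that other sections fix at 7 days, so part of the 7-day on-treatment safety period can go unsolicited

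*Protocol*

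**What the plan says.** **The rule that holds Visit 99 to the calendar.** The Flow Chart places Visit 98 on Day 169 with a window of 7 days either way, and Visit 99 on Day 176 with no window of its own. Footnote A covers what follows: "If a visit window (+/- 7 days: i.e., 1 day to 7 days) is used after randomisation", the patient should be back on schedule by the next visit, and "the number of visit window days used must be subtracted from the upcoming visit". Its stated aim is that patients complete "the treatment period at approximately Day 169 and the Post-Treatment Visit at approximately Day 176". Section 6.1 says the same: "If any visit has to be rescheduled, subsequent visits should follow the original visit date schedule". Neither place exempts the Visit 98 to Visit 99 interval or gives it a minimum length. Footnote A adds that no window between Visits 98 and 99 is allowed once enrolment has been achieved.

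**The passages that fix a week.** The Synopsis gives a one-week post-treatment period. Section 3.2 justifies that week on the ground that "the pharmacodynamic effect of linagliptin only extends to about 7 days after the last dose". Section 5.2.2.2 sets the follow-up from last medication to last visit at 7 days. Section 6.2.3, under premature discontinuation between Visits 98 and 99, describes "Visit 99 (the Post-Treatment Visit that occurs 7 days after Visit 98".

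**The analysis convention.** Section 5.2.2.2 of the protocol: "Therefore all events reported within 7 days of the last trial medication will be considered on-treatment". SAP 7.8.1: "all AEs occurring between first drug intake until 7 days after last drug intake will be assigned to the randomised treatment". Protocol 7.3.3 and SAP 6.6 and 7.8.2 treat laboratory values the same way. Adverse event collection ends at the last per-protocol contact (Section 5.2.2.2). The glucose meter and eDiary are handed back at Visit 99 (Section 6.2.3).

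**The concern.** Between treatment visits the intervals are 42 days, so taking back a few days of window does no harm. Between Visits 98 and 99 the whole interval is 7 days. Each day that Visit 98 is late therefore comes out of the only off-drug follow-up the trial has. A site with a late Visit 98 cannot both keep Visit 99 on its original date and hold it a week after Visit 98.

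Two things are at stake for safety reporting:

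- The analysis counts events up to last dose + 7 days as on-treatment. If the last contact comes before that day, new events in the remaining days are not solicited, although the patient is analysed as if the full period had been observed.
- The Visit 99 laboratory sample is off-treatment for a patient on schedule. It becomes an on-treatment value, and possibly the last on-treatment value, for a patient whose Visit 98 was late. Section 6.2.3 allows additional antidiabetic therapy from one day after Visit 98, so that value may also follow a change of therapy.

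**Working it through.** **Inputs**

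- Visit intervals of 42, 42, 42, 42 and 7 days from Day 1: Flow Chart.
- Window of up to 7 days for Visit 98, with days used subtracted from the next interval: footnote A.
- Last dose on the day before Visit 98 for completers: Section 6.2.3.
- On-treatment safety period ending 7 days after last dose: protocol 5.2.2.2 and 7.3.3, SAP 7.8.1 and 7.8.2.
- Solicited collection ending at Visit 99: Sections 5.2.2.2 and 6.2.3.

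**Plan's own schedule.** 1 + 4 × 42 = 169 and 169 + 7 = 176, which agrees with the Flow Chart. On schedule, last dose is Day 168, the on-treatment period ends on Day 175, and Visit 99 falls at last dose + 8. The period is fully covered.

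**Visit 98 late by k days, Visit 99 held at Day 176**

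- Visit 98 = 169 + k; last dose = 168 + k; on-treatment period ends on Day 175 + k.
- Gap from Visit 98 to Visit 99 = 176 - (169 + k) = 7 - k.
- Last dose to Visit 99 = 176 - (168 + k) = 8 - k.
- On-treatment days after the last contact = (175 + k) - 176 = k - 1, for k ≥ 1.

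| k | Visit 98 (day) | Last dose (day) | Period ends (day) | Gap to Visit 99 | Last dose to Visit 99 | Days after last contact, of 7 |
|---|---|---|---|---|---|---|
| 0 | 169 | 168 | 175 | 7 | 8 | 0 |
| 1 | 170 | 169 | 176 | 6 | 7 | 0 |
| 3 | 172 | 171 | 178 | 4 | 5 | 2 |
| 5 | 174 | 173 | 180 | 2 | 3 | 4 |
| 6 | 175 | 174 | 181 | 1 | 2 | 5 |
| 7 | 176 | 175 | 182 | 0 | 1 | 6 |

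More than half of the 7 days is lost only at k = 5 to 7. Section 6.1 describes the window for a rescheduled visit as under 7 days. On that wording the maximum is k = 6, with a 1-day gap and 5 of 7 days lost. An early Visit 98 loses nothing: at k = -7 the gap is 14 days.

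**Laboratory status.** The Visit 99 sample is at last dose + 8 (off-treatment) for k = 0 and at last dose + 7 or less (on-treatment) for every k ≥ 1. A single day of lateness changes its classification.

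**With the 7-day interval kept.** At k = 7, Visit 99 would be on Day 176 + 7 = 183. Last dose is Day 175 and the period ends on Day 182, so all 7 days are covered and the sample is again at last dose + 8.

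**The case against.** **The wording leaves room.** Footnote A says patients should be returned to schedule and that Visit 99 is at approximately Day 176. The sentence about a Visit 98 to Visit 99 window can be read as letting that interval flex until enrolment closes, so a site could keep the 7 days. This stands as a possible reading. It does not remove the problem, because the subtraction itself is worded as mandatory, Section 6.1 repeats it without exception, and sites may differ in what they do.

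**Fewer passages conflict than it seems.** The instructions in Sections 3.3.4.1 and 6.2.2 to return one week after Visit 98 concern early discontinuers, whose Visit 98 is not tied to Day 169. That stands. For completers the conflict rests on the Synopsis, Sections 3.2 and 5.2.2.2, and the general description of Visit 99 in Section 6.2.3. That description sits under a discontinuation heading.

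**Fewer patients are exposed.** Under the SAP, Japanese patients (100 of 300 planned) have Week 24 at Visit 7. Those who stay on treatment have no residual period added at Week 24 (SAP 6.6, 6.7 and 7.8). Patients reaching Visit 98 after enrolment closes are also outside the problem. Both limits stand. The enrolment clause is only a partial protection: Section 3.3 foresees other countries stopping recruitment while Japan continues, so non-Japanese patients can finish before the overall target is met.

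**The loss is small.** At worst it is 6 of 182 on-treatment days (175 + 7), or about 3%, under a rule that applies to both arms and in analyses that are mainly descriptive. Adverse events persisting at Visit 99 are followed for up to 7 days (Section 3.1), and later serious events are reportable if the investigator learns of them and considers them relevant (Section 5.2.2.2). This stands as to size. What remains is that new-onset events are not solicited in the uncovered days.

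**Conclusion.** The contradiction is real and the arithmetic is simple. For a non-Japanese completer with Visit 98 k days late, finishing before enrolment closes, footnote A and Section 6.1 as written leave 7-k days to Visit 99 and put k-1 of the 7 residual-effect days after the last contact. The effect is modest: some under-ascertainment of new adverse events and inconsistent classification of Visit 99 laboratory samples, in both arms. The number of late visits is not in the documents, so the share of patients affected cannot be stated.

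The result assumes that Visit 99 is held at exactly Day 176 and that last dose is the day before Visit 98.

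A reader might infer three stronger points, which the documents do not support:

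- *Most of the residual period is generally lost, or Visits 98 and 99 generally coincide.* Most of it is lost only at k = 5 to 7. The same-day case needs k = 7, which footnote A allows but Section 6.1 does not.
- *The efficacy results are compromised.* Week 24 HbA1c does not depend on Visit 99. The secondary hypoglycaemia endpoint for non-Japanese completers stops one day before the medication stop date (SAP 7.5.2).
- *The SAP needs a rule barring Visit 99 samples as the last on-treatment value.* Counting values within 7 days of last dose is a deliberate convention (SAP 6.6 and 7.8.2). The question largely disappears once Visit 99 falls at last dose + 8.

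**What to change.** Reconcile footnote A and Section 6.1 with the one-week period in the Synopsis and Section 3.2, the 7-day follow-up in Section 5.2.2.2 and the timing of Visit 99 in Section 6.2.3. One way is to state in both places that the subtract-the-window rule does not shorten the interval between Visit 98 and Visit 99, so that the last contact is not earlier than last dose + 7 days. The same edit should settle whether the window is up to 7 days or under 7 days. No SAP change is needed.

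The cost is one sentence in the footnote and one in Section 6.1. The last visit moves by up to 7 days for patients whose Visit 98 is late, which could delay last patient out by the same amount.
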